HB-adMSCs is to be administered as an IV infusion. Each 30-mL syringe contains 2×10^8 cells suspended in 20 ml of sterile saline, meant to be diluted in a volume of 250 mL. Each syringe of HB-adMSCs is specific for each patient (autologous). Each syringe will be provided by Hope Biosciences on the day of the infusion after all quality control essays have been performed and the results are within normal range.

Instructions for Administration

The designated study staff will administer the investigational product in the following manner:

- Prior to administration, visually inspect the infusion solution for particulates. If foreign particles are present, do not use the solution.
- Emergency equipment, such as epinephrine, antihistamines, and corticosteroids must be available in the event of infusion-related reactions.
- Start IV administration after dilution.
- Administer the infusion solution over a period of 1h. Observe the patient for at least 1 hour post-infusion for acute infusion-related reactions, including anaphylaxis. See Appendix 1 for guidelines on diagnosing anaphylaxis.
- Do not store or reuse any unused portion of the infusion solution. Any unused product or waste material should be disposed.
- Volume of study drug infused, start times, and stop times will be recorded. If any portion of the infusion (cell solution) is discarded, the reason will be recorded in the CRF.
- The patient will be monitored for a total of 2 hours from drug exposure to discharge.
 - a. During the Investigational product administration (1 hour) vital signs will be measured at minute 0, 15, 30 and 45.
 - b. Post infusion, vital signs will be measured at minute 0, 30, and 60.

Investigational Product Assignment and Infusion Schedule.

Each patient will be allocated a unique subject number at screening and will retain this number throughout the study.

The Investigational Product is to be administered to all eligible, enrolled patients by intravenous infusion at a dose of 2×10^8 cells at weeks 0, 2, 6, 10 and 14. Every effort should be made to adhere to the dosing schedule. However, a scheduled infusion should not be administered if a patient has an ongoing AE that, in the Investigator's opinion, warrants holding the infusion.

Prior and concomitant conditions

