Vital signs (body temperature, pulse, oxygen saturation, systolic and diastolic blood pressure measurements) will be evaluated at the visits indicated in the schedule of assessments. It is important that all vital signs be measured after the patient has been resting in a sitting position for at least 5 minutes. Blood pressure measurements are to be taken in the same arm for the duration of the study. Body weight (without coats and shoes) will be recorded whenever vital signs are recorded, and height (without shoes) will be recorded at Infusion 1 (baseline) only.

Vital sign measurements will be repeated if clinically significant or machine/equipment errors occur. Out-of-range blood pressure and pulse measurements will be repeated at the Investigator's discretion. Any confirmed, clinically significant vital sign measurements will be recorded as AEs and followed up as such.

Physical Examination

A complete physical examination (head, eyes, ears, nose, throat, heart, lungs, abdomen, skin, cervical and axillary lymph nodes, neurological, and musculoskeletal systems) will be performed at Infusion 1 (Baseline).

A limited physical examination to verify continued patient eligibility and to follow up any change in medical history will be performed at the visits indicated in the schedule of assessments. Symptom-driven physical examinations will be performed as clinically indicated at any study visit. All changes not present at baseline or described in the past medical history and identified as clinically noteworthy will be recorded as AEs.

Clinical Laboratory Parameters

The Investigator must review all laboratory reports and document the review. Any laboratory test result or change considered by the Investigator to be clinically significant should be considered an AE and recorded in the AE CRF. Clinically significant abnormal values occurring during the study will be followed until repeat test results return to normal, stabilize, or are no longer clinically significant.

Laboratory tests to be performed during the study:

Complete Blood Count with Differential	Il-10
Chemistry	IL-6
Coagulation study (PTT/PT/INR)	Tumor Necrosis Factor alpha
C Reactive Protein	Rapid Antibody Test COVID-19

Adverse Events

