4. An infusion related, sustained (over 3 minutes) episode of hypoxia (SaO₂ of less than 80%).
5. Any Grade 4-5 Adverse Event as defined in the NCI CTCAE v4.0 and determined to be temporally related to the HB-adMSC infusion by the Medical Safety Monitor and/or DSMB.

After such review, resumption of dosing may be considered, including consideration for any prophylactic interventions (e.g. antihistamines or corticosteroids for injection site reactions).

Regarding SARS-CoV-2 infection, participants will be monitored for vital signs and physical examination at every visit. If the PI suspects possible COVID-19, it is at the PI's discretion to order testing. In the event the participant test results are positive for COVID-19, they will be allowed to complete treatment with quarantine site infusion visits only.

Protocol Deviations

An Investigator may not knowingly deviate from the study protocol without prior approval by Hope Biosciences and/or the IRB unless the deviations are necessary under emergency circumstances to protect the rights, safety, or well-being of human subjects or the scientific integrity of the clinical investigation. Deviations must be documented and promptly reported to Hope Biosciences and, if applicable, to the IRB providing oversight of the study.

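### Stopping rule 4 turns on saturation below 80% for over 3 minutes, but the specified readings are 15 to 30 minutes apart, so a short episode that is not clinically evident can go unseen

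*Protocol*

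**What the plan says.** Item 4 of the Protocol's Study Stopping Rules is "An infusion related, sustained (over 3 minutes) episode of hypoxia", with saturation under 80%. Meeting any item on that list halts enrollment and sends the study to a DSMB safety review, with closure possible.

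Saturation enters through the section Vital Signs, Height, and Weight: "Vital signs (body temperature, pulse, oxygen saturation, systolic and diastolic blood pressure measurements) will be evaluated at the visits". Instructions for Administration sets the timing. During the one-hour infusion, "vital signs will be measured at minute 0, 15, 30 and 45"; then "Post infusion, vital signs will be measured at minute 0, 30, and 60". That section does not list the vital signs again. Reading saturation into every timed set is the natural interpretation, and the one more favourable to the plan.

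Three other provisions bear on the point:

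- Attendance and observation (Instructions for Administration): "The patient will be monitored for a total of 2 hours from drug exposure to discharge" and "Observe the patient for at least 1 hour post-infusion for acute infusion-related reactions, including anaphylaxis". The Infusion Visits section repeats the duty to watch for adverse events and reactions.
- Repeats (Vital Signs, Height, and Weight): "Vital sign measurements will be repeated if clinically significant or machine/equipment errors occur". No interval is given.
- Follow-up (same section): "Any confirmed, clinically significant vital sign measurements will be recorded as AEs and followed up as such". The Serious Adverse Events section requires the duration of each AE to be recorded.

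Neither document specifies continuous oximetry.

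**The concern.** The rule sets a duration criterion of 3 minutes, and the only specified measurement has gaps of 15 and 30 minutes. An episode that meets the rule can fall wholly inside one gap. The repeat and follow-up provisions start from a reading that is already abnormal, so they cannot find an episode that no reading touched.

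Rule 4 is also the only numeric saturation trigger in the documents. The Infusion Stopping Rules give limits for temperature and blood pressure but none for saturation.

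The stake is safety during dosing. The plan is for 55 patients with five infusions each, up to 55 × 5 = 275 infusions. Eligibility includes people aged 65 or over and people with COPD, asthma or heart disease, and participants who test positive may go on receiving infusions at a quarantine site. A missed episode means no halt to enrollment and no DSMB review under rule 4. A later statement that rule 4 was never met would carry little weight for short episodes.

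**Working it through.** The documents give no detection probability, so there is no figure of theirs to reproduce. The timetable agrees with itself: 1 hour of infusion plus 1 hour of observation is the stated 2 hours.

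**Inputs from the Protocol.** Readings at 0, 15, 30, 45, 60, 90 and 120 minutes from infusion start, where post-infusion minute 0 is minute 60. The gap G is 15 minutes in the infusion hour and 30 in the observation hour. A qualifying episode lasts more than 3 minutes.

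**Assumptions, not in the documents.** Onset is uniform within each hour, and only scheduled readings count. The documents give no distribution of episode length L, so results are shown by length.

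**Formula.** A reading falls inside the episode with probability min(L/G, 1), so the share missed is 1 − min(L/G, 1). It passes 50% when L is below G/2: 15/2 = 7.5 minutes in the infusion hour and 30/2 = 15 minutes in the observation hour.

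| Episode length | Missed, infusion hour (G = 15) | Missed, observation hour (G = 30) |
|---|---|---|
| 3 min (limiting case) | 1 − 3/15 = 80% | 1 − 3/30 = 90% |
| 5 min | 1 − 5/15 = 67% | 1 − 5/30 = 83% |
| 7.5 min | 1 − 7.5/15 = 50% | 1 − 7.5/30 = 75% |
| 10 min | 1 − 10/15 = 33% | 1 − 10/30 = 67% |
| 15 min | 0% | 1 − 15/30 = 50% |
| 30 min | 0% | 0% |

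The 3-minute row is the edge of the rule, which requires more than 3 minutes. The 5- and 10-minute rows are the ones to use. A simulation with 400,000 onsets per case agreed to within 0.002.

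**Whole 2 hours.** Six readings (15 to 120) each catch an onset interval of length L, so for L up to 15 the share caught is 6L/120. At 5 minutes that is 30/120 = 25% (75% missed); at 10 minutes it is 60/120 = 50% (50% missed).

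**Sensitivity to the assumptions, at 5 and 10 minutes.**

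- Onset twice as likely in the infusion hour: (2 × 67% + 83%)/3 = 72% and (2 × 33% + 67%)/3 = 44% missed.
- Whole episode required to lie inside the 120 minutes: five readings (15 to 90) can catch it, so caught = 5L/(120 − L), which is 25/115 = 22% and 50/110 = 45%. Missed: 78% and 55%.
- Longer infusion: 20 mL of cells in 250 mL of saline at the SAP's 250 mL/hr takes 270/250 × 60 = 64.8 minutes. Infusion-period misses are 1 − 20/64.8 = 69% and 1 − 40/64.8 = 38%.
- Clustered onset: every 10-minute episode that starts after minute 0 and before minute 5 ends before the minute-15 reading and is missed. Every 5-minute episode that starts in the 5 minutes before a reading is caught.

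**Allowing for staff observation.** If staff notice a fraction q of the episodes that fall between readings, missed = (1 − caught)(1 − q). Over the whole 2 hours, at 5 and 10 minutes, q = 0.5 gives 38% and 25%; q = 0.8 gives 15% and 10%. Both values of q are illustrative; the documents support neither.

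**Timing an episode that is seen.** Two scheduled readings cannot both fall in an episode shorter than 15 minutes (infusion hour) or 30 minutes (observation hour). For these, the 3-minute duration can be shown only by an unscheduled repeat.

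**The case against.** The strongest answer is that the percentages describe scheduled readings alone, which is not the plan. The patient is attended for 2 hours, staff are told to look for reactions, extra readings are not prohibited, and a significant reading must be repeated and followed up. Rule 3 (any event judged to contraindicate further dosing) and rule 5 (a Grade 4 or 5 event temporally related to the infusion) can act without a 3-minute duration. Intermittent vital signs with observation is a choice about monitoring intensity.

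Most of this stands, and it narrows the point to episodes that are short, fall between readings and are not clinically evident. The documents do not say how common these are. The answer does not close the gap, because every one of those routes needs someone first to notice the episode or a reading to catch it.

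Four stronger inferences are tempting, and the documents do not support them:

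- **That rule 4 cannot operate.** Observation and the repeat requirement can both bring it into play. It is poorly measured, not unusable.
- **That the table gives upper bounds on the miss rate.** Requiring the episode to lie inside the 2 hours, or lengthening the infusion, raises the figures, and clustered onset can move them either way.
- **That 80% to 90% of qualifying episodes are missed.** Those figures belong to exactly 3 minutes, which does not meet the rule.
- **That a missed episode certainly bypasses suspension of dosing.** The Study Alteration Rules suspend administration for events they say are listed below, but that section has no list of its own and refers events to the Internal Monitoring Committee, not the DSMB. Suspension follows only if those rules are read as covering rule 4.

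**Conclusion.** The point holds in a limited form. Followed exactly as written, the plan can miss a qualifying episode that staff do not notice. Under uniform onset, the schedule alone misses 67% of 5-minute and 33% of 10-minute episodes in the infusion hour, and 83% and 67% in the observation hour. These describe the schedule and not the trial's overall safety monitoring, whose miss rate cannot be derived from the documents.

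The firm consequence is a missed halt to enrollment and a missed DSMB review. No SAP summary depends on rule 4. Because the harm is confined to short, clinically silent episodes of unknown frequency, the change lies between one to consider and one that should be made. It is justified mainly because it is inexpensive and makes a safety trigger measurable on the time scale that the Protocol itself chose. Confidence is medium.

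**What to change.** In Instructions for Administration, require the pulse oximeter to stay on continuously from infusion start to the end of the 60-minute observation, including infusions at quarantine sites. For any reading below 80% that persists after a probe check, record the lowest value and the time below 80% in the CRF.

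The cost is Protocol wording and two CRF entries. The patient is already attended for these 2 hours and saturation is already measured, so no staff or invasive procedure is added. The downsides are artefact alarms to review, which the probe check is meant to limit, and the need at each infusion site for an oximeter that can stay on. The documents do not confirm that one is available.

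A useful addition is to repeat any reading below 80% at once and follow it for more than 3 minutes. This puts a time on the existing repeat requirement and needs no new equipment, but it does not find episodes between readings. With scheduled readings alone over the 2 hours, it would show more than 3 minutes below 80% in a share 6(L − 3)/120 of episodes: 12/120 = 10% at 5 minutes, 42/120 = 35% at 10 and 72/120 = 60% at 15. It should not replace continuous oximetry.

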1. INTRODUCTION

The purpose of this Statistical Analysis Plan (SAP) is to describe the analyses to be included in the Clinical Study Report for Protocol HBCOVID-01. Details of the planned final analysis provided.

Additional detail with regards to data handling conversions and the specification of the data displays will be provided in the Programming Specifications (PS) document.

2. SUMMARY OF KEY PROTOCOL INFORMATION

2.1. Study Objective(s), Estimand(s) and Endpoint(s)

Objectives	Endpoints
Primary Objective	Primary Endpoint

 To investigate the efficacy of HB-adMSCs in providing immune support against development of Coronavirus Disease by incidence of hospitalization for COVID-19, incidence of symptoms associated with COVID-19 (ie., fever, shortness of breath/difficulty breathing, and/or cough), and severity of COVID-19 associated symptoms ((fever 38C or higher, cough, shortness of breath/difficulty breathing). 	
 Incidence of hospitalization for COVID-19. Incidence of symptoms associated with COVID-19
Secondary Objective	Secondary Endpoint

 To investigate the efficacy of HB-adMSCs in the prevention of upper and lower respiratory infections in a high-risk population. 	
 Absence of upper/lower respiratory infections (with hospitalization criteria) up to 3 months post infusions. Change from baseline in leukocyte differential Change from baseline in C-Reactive Protein Change from baseline in TNF-alpha Change from baseline in IL-6 Change from baseline in IL-10

CONFIDENTIAL**Hope Biosciences****HBCOV01**

Objectives	Endpoints
	
• Clinically significant changes in laboratory values, vital signs, weight, and physical examination results.• Incidence of Adverse Events (AEs) and serious AEs (SAEs) related to the drug

2.2. Study Design

Overview of Study Design and Key Features	
This phase II, open label, single-center, safety and efficacy study is designed to evaluate HB-adMSCs to support immunity against Coronavirus Disease.	
Design Features	
The trial includes,
 
 • There is a screening period of up to 14 days • A 14-week treatment period while on HB-adMSCs 
 ▪ Infusion 1 (Week 0), Infusion 2 (Week 2), Infusion 3 (Week 6), Infusion 4 (Week 10) and Infusion 5 (Week 14) • A safety Follow-up periods and end of the study or early discontinuation visit. 
 ▪ Follow up week of 18 and 22 and end of study at Week 26 • 55 Subjects
Study Intervention	
 • Intervention: HB-adMSCs (Hope Biosciences adipose derived mesenchymal stem cells) 
 ▪ Dose: 2×10^8 cells suspended in 20 ml sterile saline ▪ Route: Intravenous ▪ Regimen: Weeks 0, 2, 6, 10 and 14. ▪ 83 gts/min (250 mL/hr) • Study treatment details, 
 ▪ Each syringe contains 20 ml of cells solution with 2×10^8 cells (+20%). The syringe content is to be diluted in 250 mL of 0.9% sodium chloride.
Study Intervention Assignment	
 • All participants receive HB-adMSCs
Interim Analysis	
 • No interim analysis will be performed in this study

3. STATISTICAL HYPOTHESES

No formal statistical hypothesis testing performed.

3.1. Multiplicity Adjustment

No multiplicity adjustments will be performed as this is early phase study and no formal statistical hypothesis testing performed.

4. ANALYSIS SETS

Population	Definition / Criteria	Analyses Evaluated
Safety analysis set	
 • All subjects that receive at least one HB-adMSC infusion will be included in safety analysis. 	
 • Safety • Study Population
Efficacy analysis set	
 • All subjects that receive all 5 infusions of HB-adMSCs will be included in efficacy analysis. 	
 • Efficacy
Screened Population	
 • This population consists of all subjects who signed an ICF to participate in the clinical trial. • This population will be used for summarizing screening failures and reasons for screening failures. 	
 • Study Population

5. STATISTICAL ANALYSES

5.1. General Considerations

The final planned primary analyses will be performed after the completion of the following sequential steps:

1. All participants have completed (or withdrawn from) the study as defined in the protocol.
2. All required database cleaning activities have been completed and final database release and database lock has been declared by Data Management.

5.1.1. General Methodology

All continuous measurements will be summarised descriptively at each visit by treatment using observed data.

Summary of continuous variables will be presented using N, Mean, Standard Error of mean (SE), Standard Deviation (SD), Median and Range (Minimum and Maximum). The categorical variables will be presented using number and percentage based on N.

For measurements over time mean values will be plotted to explore the trajectory over time. Observed data will be used as the basis for plotting data along with bars as standard error (SE) or Standard Deviation (SD), if not otherwise specified.

Study population analyses including analyses of subject disposition, demographic and baseline characteristics.

Disposition summary includes, subject screened, and disposition at end of study – Week 26 along with reasons for withdrawals. Subjects in different analysis populations also will be presented.

The screen failure table includes total number of screened subjects and reasons. The percentage in the screen failure table will be calculated based on total number of screened subjects as denominator.

5.1.2. Baseline Definitions

For all endpoints, the baseline value will be the latest pre-treatment assessment visit with a non-missing value. i.e., If an assessment has been made both at screening visit (Visit 1) and Week 0 infusion 1 visit (Visit 2, Week 0), the value from the Week 0 visit is used as the baseline value. If the value measured at the Week 0 visit is missing and the assessment also has been made at screening, then the screening value is used as the baseline value.

Unless otherwise stated, if baseline data is missing no derivation will be performed and baseline will be set to missing.

5.2.1. Definition of endpoint(s)

Objectives	Endpoints
Primary Objective	Primary Endpoint
To investigate the efficacy of HB-adMSCs in providing immune support against development of Coronavirus Disease by incidence of hospitalization for COVID-19, incidence of symptoms associated with COVID-19 (ie., fever, shortness of breath/difficulty breathing, and/or cough), and severity of COVID-	Incidence of hospitalization for COVID-19. Incidence of symptoms associated with COVID-19

CONFIDENTIAL**Hope Biosciences**

HBCOV01

Objectives	Endpoints
19 associated symptoms ((fever 38C or higher, cough, shortness of breath/difficulty breathing).	

5.2.2. Main analytical approach

Endpoint/Variables

• Incidence of COVID-19 symptoms and Hospitalizations due to COVID-19 symptoms after Week 26 end of study
Model Specification/analysis method

• Incidence COVID-19 symptoms and Hospitalizations due to COVID-19 symptoms after Week 26 is summarized as counts and percentage

